Cell Transplantation Institute
T: [contact] [name]
F: [contact]
Email: [contact]

Biostatistician/Co-Investigator

[name]

City of Hope National Medical
Center
Division of Biostatistics
T: [contact]
Email: [contact]

Co-Investigator

[name]

City of Hope National Medical Center
Hematologic Malignancies and Stem
Cell Transplantation Institute
T: [contact] [name]
F: [name]
Email: [contact]

Co-Investigator

[name]

City of Hope National Medical Center
and Beckman Research Institute
Hematologic Malignancies and Stem
Cell Transplantation Institute
T: [contact] [name]
F: [name]
Email: [contact]

Co-Investigator

[name]

City of Hope Beckman Research
Institute
Department of Cancer Biology
T: [contact] [name]
F: [contact]
Email: [contact]

Protocol Development Scientist

[name]

City of Hope National Medical Center
Dept. of Clinical and Translational
Project Development
T: [contact]
Email: [contact]

Agent(s):

8-chloro-adenosine

IND#:

[figure not shown]
118750

IND holder:

City of Hope

EXPERIMENTAL DESIGN SCHEMA

This is a phase I/II trial of 8-chloro adenosine when given as a single agent in patients with relapsed or refractory acute myeloid leukemia.

*Six of the 9 initial participants included in the phase II will be phase I participants treated at the RP2D.

**In the phase II, if 0 responses are seen in the first 9 participants treated at the RP2D, the study will be terminated.

If at least 1 participant responds, the phase to continue to enroll up to 25 participants treated at the RP2D.

[^]Participants will be hospitalized during therapy (at minimum the first 6 days of the cycle). Participants will be admitted to the telemetry unit and undergo continuous cardiac monitoring from start of treatment until 24 hours after completion of therapy during Cycles 1-4.

PROTOCOL SYNOPSIS

Protocol Title:
A Phase I/II Trial of 8-chloro-adenosine in Relapsed or Refractory Acute Myeloid Leukemia
Brief Protocol Title for the Lay Public (if applicable):
8-chloro-adenosine in patients with relapsed or refractory acute myeloid leukemia
Study Phase:
Phase I/II
Participating Sites:
Single Center: City of Hope, Duarte CA
Rationale for this Study:
8-chloro-adenosine is a derivative and active metabolite of 8-chloroadenosine 3'5'-monophosphate (8-chloro-cAMP). The latter compound has shown antitumor activity in a broad variety of cancers in preclinical studies as well as previous clinical trials. 8-chloro-adenosine has also shown antineoplastic activity in vitro and in vivo with an excellent toxicity profile in preclinical studies. 8-chloro-adenosine appears to have a novel mechanism of action. Its cytotoxic metabolite, 8-chloro-ATP induces depletion of cellular ATP stores and interferes with RNA synthesis thereby leading to apoptosis. Among all cell lines tested in vitro, 8-chloro-adenosine has been shown to be particularly active in leukemia including human AML cell lines and AML primary cells. Efficacy has recently been demonstrated in an animal model of AML. Importantly, the pathway of 8-Cl-Ado-mediated cell death appears to be p53-independent, which is especially critical considering that p53 mutations/deletions are associated with drug resistance and adverse outcomes in AML. Furthermore, 8-chloro-adenosine synergizes with the chemotherapy drugs clofarabine, cytarabine and doxorubicin in the induction of growth inhibition of human AML cells, thereby potentially expanding the therapeutic potential of this novel agent. The in vitro antileukemic activity, favorable toxicity profile and unique mechanism of action makes 8-chloro-adenosine an ideal candidate for testing in early phase clinical trials in AML.
Objectives:

Phase I
 
Primary Objective
 
To determine the maximum tolerated dose (recommended phase II dose, RP2D) of 8-chloro-adenosine, when given as a single agent, in patients with relapsed or refractory acute myeloid leukemia.
 
To assess tolerability and safety of 8-chloro-adenosine at each dose level by evaluation of toxicities including: type, frequency, severity, attribution, time course and duration.
 
Secondary Objective
 
To evaluate for disease response to 8-chloro-adenosine in refractory/relapsed AML on each dose level tested.

Phase II

Primary Objective

To estimate the response rate and to evaluate the antitumor activity of 8-chloro-adenosine, when given as a single agent, as assessed by complete remission rate (CR+CRI) at the RP2D.

Secondary Objectives

To obtain estimates of remission duration and survival probabilities (overall and event-free).

To obtain an estimate of the overall response rate (CR+CRI+PR).

To summarize and evaluate toxicities by type, frequency, severity, attribution, time course and duration.

Clinical Pharmacology Objectives (Phase I and II)

To describe the plasma, urinary and cellular pharmacokinetics of 8-chloro-adenosine and metabolites.

To determine the impact of 8-chloro-adenosine on cellular ATP pool in AML blasts.

To assess the impact of 8-chloro-adenosine therapy on select short-lived mRNAs and corresponding proteins in circulating AML blasts.

To correlate clinical responses and toxicity with plasma/urine 8-chloro-adenosine level (PK), cellular 8-Cl-ATP (PK) and cellular ATP pool.

Exploratory Ex-Vivo Molecular Objectives (Phase I and II)

To determine the cytotoxicity of 8-chloro-adenosine toward leukemic progenitor cells in vitro.

To generate a preliminary pre-treatment RNA/miRNA signature in leukemic progenitor cells, and explore its possible association with in vitro cytotoxicity to 8-chloro-adenosine.

To explore the possible association between the preliminary RNA/miRNA signature and clinical response to 8-chloro-adenosine.

Study Design:

This study will be conducted as a single center phase I/II trial.

Participants will receive up to four cycles of study agent, and will be followed for up to 2 years after their first dose of study agent.

Phase I Design:

The phase I portion will follow a modified 3+3 design in order to evaluate toxicities associated with 8-chloro-adenosine when given as a single agent. In the absence of notable toxicity (see sections 13.2 and 13.3), four doses of 8-chloro-adenosine will be tested: 100mg/m²; 200 mg/m²; 400 mg/m² and 800 mg/m². Intermediate dose levels ('b' levels), in increments of 50% from the planned four doses, will be explored in the presence of dose limiting toxicity or unacceptable moderate toxicity. Intermediate doses are defined as follows: 150mg/m²; 300 mg/m²; and 600 mg/m².

With amendment v07, the starting dose will be: 400 mg/m² (dose level 3a).

8-chloro-adenosine will be administered as a 4 hour infusion daily for 5 days every 4 weeks; treatment cycle length is 28 days. The dose of 8-chloro-adenosine will depend on dose level assignment. The maximum tolerated dose (MTD) will be established by evaluating dose limiting

toxicity (DLT) during cycle 1. The highest dose level that produces $\leq 1/6$ DLTs in cycle 1 will be the MTD.

The recommended phase II dose (RP2D) will generally be the MTD, but it may be less than the MTD based on a review of available data/cumulative toxicities and activity.

Phase II Design:

The phase II portion of this study will implement a Gehan two-stage design to estimate the response rate and to evaluate the activity of 8-chloro-adenosine when given as a single agent (Gehan, 1961). The phase II portion of the study is expected to enroll a minimum of 9 and a maximum of 25 patients. Patients treated at the RP2D in the phase I portion of the study, who receive at least 2 cycles of treatment, will count toward the 25 patients required. The sample size is based on the desire to estimate the response rate with at most 10% standard error, and early stopping if the treatment is unexpectedly ineffective.

At stage 1, 9 patients will be entered on the study. If 0 responses are seen in the first 9 patients treated, the study will be terminated and the true regimen response will be declared $\leq 30\%$. If at least 1 patient responds, the trial will continue to the second stage. Because patients treated during the phase I portion of the trial at the dose selected for the phase II trial will be counted ($n=6$), only 3 additional patients will be enrolled at stage 1. Under this design if the study agent is $>30\%$ effective, there would be 96% chance of at least one success.

At stage 2, 16 additional patients will be entered. This accrual provides for estimation of the response rate with no more than 10% standard error.

Endpoints:

Phase I:

The primary endpoint is toxicity. Toxicity will be graded according to the NCI-Common Terminology Criteria for Adverse Events version 4.03. Dose limiting toxicity (DLT) and moderate toxicity are defined in section 13.2 of the protocol. Note: The phase II portion of the study will use the DLT definition to define unacceptable toxicity. The MTD will be based on the assessment of DLT during cycle 1. All patients who are not evaluable for dose limiting toxicity will be replaced.

Phase II:

The primary endpoint is complete remission rate (CR/CRi) and is based on the Döhner et al. 2010 criteria²⁴. Response will be assessed at the end of each cycle/just prior to the start of each cycle. Secondary endpoints include: remission duration, survival (overall and event-free) and toxicity.

Clinical Pharmacology Endpoints:

- For plasma PK, levels of 8-chloro-adenosine, its deaminated metabolite, 8-chloro-inosine, and its base 8-chloro-adenine will be quantitated in plasma during 5 days of therapy.
- For cellular PK, concentrations of 8-chloro-adenosine and 8-chloro-ATP will be quantitated in circulating leukemia cells in the peripheral blood.
- For urine PK, levels of 8-chloro-adenosine, its deaminated metabolite, 8-chloro-Inosine, and its base 8-chloro-adenine will be quantitated in urine during the first 24 hours of therapy.
- For PD, the impact of therapy on endogenous ATP pools, as well as the effect on short-lived mRNA transcripts and proteins will be analyzed in circulating acute leukemia blasts.

Sample Size:

The overall expected study sample size is 43.
 
While the phase I study is expected to enroll and treat 15 patients (dose levels 1-3(a) to enroll/treat 3 patients each for a total of 9, and another 6 at dose level 4a-assuming the 800mgm² dose is well tolerated), a maximum of 24 patients could be treated (6 patients treated at each of the four dose levels –‘a’ levels) assuming intermediate doses are not pursued.
 
The phase II portion of the study is expected to enroll a minimum of 9 (6 of whom will be from the phase I) and a maximum of 25 patients.

Estimated Duration of the Study

Accrual, for both phases, is expected to be completed in 70 months. Follow up of each patient will be for a maximum of 2 years; the maximum study duration is 8 years.

Summary of Subject Eligibility Criteria:


Inclusion criteria
 
- Diagnosis of AML as per WHO Classification of Hematologic Neoplasms.- Meets one of the three criteria:
o Relapsed AML who have failed at least 1 line of salvage therapyo De novo AML who have not achieved CR after 2 lines of therapyo AML evolving from MDS or myeloproliferative disorder who have failed hypomethylating agent and/or induction chemotherapyo Patients who have relapsed after allogeneic HCT are eligible if they are at least 3 months after HCT, do not have active GVHD and are off immunosuppression except for maintenance dose of steroids (prednisone 10 mg/day or less).- At least 2 weeks from prior chemotherapy or radiation therapy to time of start of treatment, except for hydroxyurea or corticosteroid therapy which may be continued through Cycle 1 of Phase 1 portion of protocol.- Age \geq 18 and life expectancy $>$ 3 months.- ECOG status of 0-2.- AST and ALT \leq 2.5 x ULN- QTc \leq 480 ms- Calculated creatinine clearance (CrCl) \geq 50 mL/min per 24 hour urine 
Exclusion criteria
 
- Expected to undergo HCT within 120 days of enrollment.- Current or planned use of agents that prolong or suspected to prolong QTc- Diagnosis of acute promyelocytic leukemia- Active central nervous system leukemia- Active fungal infection- History of heart failure or cardiac arrhythmia- Females who are pregnant or lactating.

Investigational Product Dosage and Administration:
 
Four doses of 8-chloro-adenosine may be tested (dose level 1a: 100mg/m²; dose level 2a: 200 mg/m²; dose level 3a: 400 mg/m² and dose level 4a: 800 mg/m²
 
Intermediate dose levels –‘b’ levels, in increments of 50% from the planned four doses, will be explored in the presence of dose limiting toxicity or unacceptable moderate toxicity. Intermediate doses are defined as follows: 150mg/m²; 300 mg/m²; and 600 mg/m².
 
With amendment v07, the starting dose will be 400 mg/m² (dose level 3a).
 
8-chloro-adenosine will be administered as a 4-hour intravenous infusion for 5 days every 28 days). There will be no intra patient dose escalation.


Clinical Observations and Tests to be Performed:
 
Clinical observations will include tolerance as well as response to treatment (see study calendar). Baseline studies will include a history and physical,12-lead EKG, bone marrow biopsy as well as a laboratory evaluation to include CBC with differential, comprehensive chemistry panel (to include LDH, magnesium, phosphorus and uric acid) and urinalysis. Response will be assessed at the end of every cycle. Subjects will be evaluated through weekly clinic visits and physical exams as well as laboratory tests to include CBC with differential, comprehensive chemistry panel and labs.
 
12-lead EKG will be performed at pre-infusion and post-end of infusion on days the study drug is administered for all cycles.
 
Patients will undergo continuous cardiac monitoring in telemetry unit from start of treatment until 24 hours after completion of treatment during Cycles 1-4.
 
Blood and urine samples will be collected for pharmacokinetic and pharmacodynamic correlative studies. In addition, additional bone marrow will be collected at the time of bone marrow biopsy for planned correlative studies and future studies.


Statistical Considerations:
 
Study Design
 
Phase I: The primary objective of the phase I study is to determine the recommended phase II dose (RP2D) of 8-chloro-adenosine when given as a single agent, in patients with relapsed or refractory acute myeloid or lymphoblastic leukemia. The phase I study will follow a modified 3+3 design for enrollment with dose escalation, or expansion of a cohort on the basis of the occurrence of dose limiting toxicities (DLTs) during cycle 1. This modified design involves an initial accelerated dose escalation stage (dose-doubling from an initial dose of 100mg/m² to 800mg/m²) that may be ended by a single DLT in cycle 1 or two occurrences of ‘moderate’ treatment-related toxicity. During the initial accelerated stage of accrual, cohorts of up to 3 patients will be enrolled and the dose level will be escalated by increments of 100%. The accelerated stage will end when two patients encounter moderate toxicity or when one patient encounters DLT during cycle 1. At the conclusion of the accelerated stage, the dose escalation will occur according to the standard 3+3 rules: The highest dose level that produces $\leq 1/6$ DLTs in cycle 1 will be the maximum tolerated dose (MTD). The RP2D of 8-chloro-adenosine will generally be the MTD, but it may be less than the MTD based on a review of available data/cumulative toxicities from phase I. The RP2D identified in the phase I portion of the study will be brought forward for further activity evaluation in the phase II portion.

Phase I/ Evaluable for Toxicity: Patients will be considered evaluable for toxicity if they receive any study drug. To be evaluable in the context of dose escalation, a patient must receive at least 80% of 8-chloro-adenosine and be followed for at least 28 days during cycle 1 or experience a DLT during the first cycle of therapy. All patients who are not evaluable for dose limiting toxicity will be replaced. Patients who are replaced with a moderate toxicity will be used in the decision to stop the accelerated dose-doubling stage.

Phase II: The primary objective is to estimate the response rate and to evaluate the antitumor activity of 8-chloro-adenosine, in patients with relapsed or refractory acute myeloid or lymphoblastic leukemia. The primary endpoint is complete remission rate (CR/CRI) and is based on the Döhner, 2010 criteria²⁴. A cycle of treatment is 28 days. Each patient's disease status will be evaluated at baseline. Response will be assessed at the end of each cycle/just prior to the start of each cycle.

The phase II portion of this study will implement a Gehan two-stage design to estimate the response rate and to evaluate the activity of 8-chloro-adenosine when given as a single agent. The phase II portion of the study is expected to enroll a minimum of 9 and a maximum of 25 patients. The six patients treated at the RP2D in the phase I portion of the study will count toward the 25 patients required; given this, we expect to enroll only 19 new patients on the phase II trial. The sample size is based on the desire to estimate the response rate with at most 10% standard error, and early stopping if the treatment is unexpectedly ineffective.

At stage 1, 9 patients will be entered on the study. If 0 responses are seen in the first 9 patients treated, the study will be terminated and the true regimen response will be declared $\leq 30\%$. If at least 1 patient responds, the trial will continue to the second stage. Because patients treated during the phase I portion of the trial at the dose selected for the phase II trial will be counted ($n=6$), only 3 additional patients will be enrolled at stage 1. Under this design if the study agent is $>30\%$ effective, there would be 96% chance of at least one success.

At stage 2, 16 additional patients will be entered. This accrual provides for estimation of the response rate with no more than 10% standard error.

Phase II (Evaluable for Toxicity): Patients will be considered evaluable for toxicity if they receive any study drug. Patients enrolled/treated as part of the phase II study will not be replaced based on toxicity.

Phase I and II (Evaluable for Response): For the phase II portion, as part of the primary analysis, patients will be considered evaluable for response if they are eligible, have baseline disease assessments, and receive 2 cycles of protocol treatment or achieve a CR/CRI after 1 cycle of protocol treatment. Patients will have their response classified according to the Dohner 2010 criteria²⁴.

Sample Size

Phase I: In the phase I portion of this study, the total sample size will depend on the number of dose levels evaluated to determine the RP2D. While the phase I study is expected to enroll and treat 15 patients (dose levels 1-3 –'a' levels, to enroll/treat 3 patients each for a total of 9, and another 6 at dose level 4a-assuming the 800 mg/m^2 dose is well tolerated), a maximum of 24 patients could be treated (6 patients treated at each of the four dose levels) assuming intermediate doses are not pursued.

Phase II: The phase II portion of the study is expected to enroll a minimum of 9 and a maximum of 25 patients. The six patients treated at the RP2D in the phase I portion of the study will count toward the 25 patients required; given this, we expect to enroll only 19 new patients during the

phase II trial portion. The sample size is based on the desire to ensure a (promising) response rate of 30% is not missed.

Clinical Pharmacology (PK/PD): Pharmacokinetic (PK) analyses will be performed during Cycle 1 in all enrolled patients in Phase 1 and Phase 2 portions of this protocol. In addition, pharmacodynamic measurements will be performed during Cycle 1 in all enrolled patients in the Phase 1 and 2 portions who have ≥ 5000 circulating leukemic blasts per microliter.

Molecular Studies: For mRNA-seq, sequence reads will be mapped to the human genome (hg19) using TopHat and the frequency of Refseq genes will be counted with customized R scripts. For miRNA-seq, sequences will be adapter trimmed and aligned to hg19 genome using Novoalign, and miRNA expression level will be counted as previously described [1]. The raw counts will then be normalized and compared using the Bioconductor package “edgeR” [2]. Fold changes > 3 with a false discovery rate (FDR) < 0.05 will be considered significant. Assuming the dispersion of genes across replicates is 0.2, 12 samples in each group (responder vs. non-responder) should have 88% power to detect a 3-fold difference between groups at an FDR level of 0.05.

Safety Analysis and Stopping Rules for Excessive Toxicity

The early stopping rule for safety/toxicity will be assessed for each patient after cycle 1: the expected rate of unacceptable toxicity should not be $\geq 33\%$. Note: The phase II portion of the study will use the DLT definition to define unacceptable toxicity. If more than the specified number of patients has significant treatment related toxicities, patient accrual will be halted and a full review of the data by the Data Safety Monitoring Committee (DSMC) will be mandated. Patient accrual will not resume until approved by the DSMC to do so.

In addition, cumulative safety data will be reviewed on a quarterly basis in order to identify safety concerns that may emerge due to cumulative exposure.

Trial Statistical Analysis Plan

Patient demographic and baseline characteristics, including age, gender, medical history, and prior therapy, will be summarized using descriptive statistics. For continuous variables, descriptive statistics (number [n], mean, standard deviation, standard error, median (range) will be provided. For categorical variables, patient counts and percentages will be provided.

Phase I Analysis: Observed toxicities will be summarized in terms of type (organ affected or laboratory determination), severity, time of onset, duration, probable association with the study treatment and reversibility or outcome. Baseline information (e.g. the extent/type of prior therapy) and demographic information will be presented as well to describe the patients treated in this study.

Phase II Analysis: The complete remission rate (CR+CRi) will be calculated as the percent of evaluable patients; exact 95% confidence intervals will be calculated for these estimates. Response rates will also be evaluated based on number and type of prior therapy(ies). Time to response, duration of response, and survival will be estimated using the product-limit method of Kaplan and Meier.

Clinical Pharmacology Analysis: Plasma, urinary and cellular PK of 8-chloro-adenosine and metabolites will be quantitated as continual measurement variables. Descriptive statistics and graphical displays will be used to summarize levels of serum/urine 8-chloro-adenosine and its metabolites at each time point and to evaluate changes over time. A paired t-test will be used to determine if there is a statistically significant change. Similar methods will be used to assess the PD impact of 8-chloro-adenosine on the cellular ATP pool and select short-lived mRNAs including corresponding proteins in AML blasts. Protein and mRNA levels will be summarized descriptively

using means, medians, standard deviations and ranges. Summary statistics of the PK/PD parameters for the population will be derived from the parameters obtained from the individual patients. Results will also be summarized in terms of response and toxicity. To determine if there are dose-dependent changes in 8-Cl-ATP and 8-chloro-adenosine (when administered ex vivo), summary statistics and graphical displays will be generated to descriptively compare accumulation of 8-Cl-ATP and endogenous ATP levels in circulating AML blasts over 5 doses.

Molecular Studies Analysis: Gene ontology (GO) and pathways will be analyzed using DAVID (Database for Annotation, Visualization, and Integrated Discovery), an online bioinformatic resource for functional interpretation of large lists of genes. Pathways and GO that correlate with response will be sorted by their multiple comparison adjusted p value. Potential miRNA targets will be identified using TargetScan and their functional annotation will be done using DAVID. All summaries will be exploratory in nature, with the goal of developing further questions regarding the modulation of therapy, or regarding reasons for efficacy or lack of efficacy.

Sponsor/Licensee:

Investigator Initiated: City of Hope

Case Report Forms

Medidata RAVE® Electronic Data Capture system.

TABLE OF CONTENTS

SECTION	PAGE
Experimental Design Schema	2
Protocol Synopsis.....	3
Table of Contents	11
Abbreviations.....	14
1.0 Goals and Objectives (Scientific Aims)	15
1.1 Primary Objectives	15
1.2 Secondary Objectives.....	15
1.3 Clinical Pharmacology Objectives (Phase I and II).....	15
1.4 Exploratory Ex-Vivo Molecular Objectives (Phase I and II)	15
2.0 Background.....	16
2.1 Acute Myeloid Leukemia.....	16
2.2 8-Chloro-adenosine.....	16
2.3 Overview and Rationale of Study Design	16

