1.2 Secondary Objectives

Phase I:

To evaluate for disease response to 8-chloro-adenosine in refractory/relapsed AML on each dose level tested.

Phase II:

To obtain estimates of remission duration and survival probabilities (overall and event-free).

To obtain an estimate of the overall response rate (CR+CRi+PR).

To summarize and evaluate toxicities by type, frequency, severity, attribution, time course and duration.

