Phase I (Evaluable for Toxicity): Patients will be considered evaluable for toxicity if they receive any study drug. To be evaluable in the context of dose escalation, a patient must receive at least 80% of 8-chloro-adenosine and be followed for the full 28 days during cycle 1 or experience a DLT during the first cycle of therapy. All patients who are not evaluable for DLT will be replaced.

Phase II:

The primary objective is to estimate the response rate and to evaluate the antitumor activity of 8-chloro-adenosine, in patients with relapsed or refractory acute myeloid or lymphoblastic leukemia. The primary endpoint is complete remission rate (CR/CRI) and is based on the Döhner, 2010 criteria²⁴. A single cycle of treatment will be given in a 28 day cycle. Each patient's disease status will be evaluated at baseline. Response will be assessed at the end of each cycle/just prior to the start of each cycle.

The phase II portion of this study will implement a Gehan two-stage design to estimate the response rate and to evaluate the activity of 8-chloro-adenosine when given as a single agent [23]. The phase II portion of the study is expected to enroll a minimum of 9 and a maximum of 25 patients. The six patients treated at the RP2D in the phase I portion of the study will count toward the 25 patients required; given this, we expect to enroll only 19 new patients on the phase II trial. The sample size is based on the desire to estimate the response rate with at most 10% standard error, and early stopping if the treatment is unexpectedly ineffective.

At stage 1, 9 patients will be entered on the study. If 0 responses are seen in the first 9 patients treated, the study will be terminated and the true regimen response will be declared $\leq 30\%$. If at least 1 patient responds, the trial will continue to the second stage. Because patients treated during the phase I portion of the trial at the dose selected for the phase II trial will be counted ($n=6$), only 3 additional patients will be enrolled at stage 1. Under this design if the study agent is $>30\%$ effective, there would be 96% chance of at least one success.

At stage 2, 16 additional patients will be entered. This accrual provides for estimation of the response rate with no more than 10% standard error.

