13.4 Recommended Phase II Dose (RP2D)

The MTD will be based on the assessment of DLT during cycle 1 (see section 13.2). The MTD will be defined as the highest dose at which $\leq 1/6$ patients in a cohort experience DLT. The recommended phase II dose (RP2D) of 8-chloro-adenosine will generally be the MTD, but it may be less than the MTD based on a review of available data/cumulative toxicities from phase I.

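### The synopsis lets activity inform an RP2D below the MTD and then pools those phase I patients without allowance for selection, and the fixed count of six pooled patients is not guaranteed

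*Combined protocol and SAP*

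**What the plan says.** **Choice of the RP2D.** In the Study Design part of the synopsis the MTD is the default choice. An exception follows: "but it may be less than the MTD based on a review of available data/cumulative toxicities and activity". Section 13.4 gives the rule as: "but it may be less than the MTD based on a review of available data/cumulative toxicities from phase I". Section 13.1 and the synopsis's Statistical Considerations follow section 13.4 and do not name activity. Response data will exist for each level, because a phase I secondary objective (section 1.2) is: "To evaluate for disease response to 8-chloro-adenosine in refractory/relapsed AML on each dose level tested".

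**Pooling.** Section 13.1 states: "The six patients treated at the RP2D in the phase I portion of the study will count toward the 25 patients required", so 19 new patients are expected. At stage 1 nine patients are entered, six of them from phase I, so "only 3 additional patients will be enrolled at stage 1". The trial stops if none of the first nine responds; otherwise 16 more are entered. Section 13.7 takes the CR/CRi rate as a simple percentage of evaluable patients with an exact 95% interval. No adjustment for selection and no analysis without the phase I patients is planned.

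**Who counts.** The Study Design part of the synopsis counts a phase I patient at the RP2D only after at least two cycles. The synopsis's Statistical Considerations and sections 13.1 and 13.5 count the six without that condition.

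**The concern.** Two separate matters arise.

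First, if a lower level is chosen partly because it showed more remissions, its phase I patients are no longer an unselected sample at a dose fixed in advance. A level preferred for its CR/CRi already holds a responder. If that patient counts, the stop for no responses in nine cannot trigger on that branch. At stake are the futility protection of stage 1 and, to a lesser degree, the primary rate.

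Second, every version of the rule allows an RP2D below the MTD. Section 13.3 escalates after 0 of 3 DLTs, and the synopsis expects three patients at each of the lower planned levels. Section 13.3 expands a lower level only after two or more DLTs above it, not when a lower RP2D is chosen on review. The chosen level may therefore hold three patients rather than six, and the two-cycle condition could reduce the number further. The stated 96% and 10% standard error rest on six.

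**Working it through.** **The plan's own figures reproduce.**
- Chance of at least one response in 9 at a true 30%: 1 - 0.7^9 = 0.960.
- Maximum standard error with 25 patients: sqrt(0.25/25) = 0.100.
- Overall size: 24 + 25 - 6 = 43.

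**Effect of selection on stage 1.** The documents give no selection rule, so one is assumed:
- two candidate levels have the same true rate p;
- the MTD level has 6 patients and the lower level m = 3 or 6;
- the lower level is chosen whenever its observed rate is strictly higher;
- stage 1 is filled to nine.

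The chosen level has no responders only if both levels have none. The trial then stops with probability (1-p)^m × (1-p)^6 for phase I, times (1-p)^3 for the new patients. If both levels have none, the MTD level is chosen and three are added, so the chance of passing is 1 - (1-p)^(9+m).

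| True rate | No selection, 1-(1-p)^9 | m = 3, 1-(1-p)^12 | m = 6, 1-(1-p)^15 |
|---|---|---|---|
| 5% | 37.0% | 46.0% | 53.7% |
| 10% | 61.3% | 71.8% | 79.4% |
| 30% | 96.0% | 98.6% | 99.5% |

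If activity decides only half the time, the m = 6 figures are the midpoints: 45% at a true 5% and 70% at 10%.

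**Effect on the final rate.** A 25-patient rate exists only if stage 1 is passed, so the comparison is made among passing trials. A stopped trial has no stage-1 responders, so the mean rate among passing trials is [E(stage-1 responders)/P(pass) + 16p]/25.
- Without selection at 10%: (0.9/0.6126 + 1.6)/25 = 12.3%.
- With m = 6 at 10%, the mean phase I rate carried forward is 16.12% by exact enumeration. Stage-1 responders average 6 × 0.1612 + 0.3 = 1.267, and (1.267/0.7941 + 1.6)/25 = 12.8%.

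| True rate | No selection | m = 3 | m = 6 | Added bias (points) |
|---|---|---|---|---|
| 5% | 8.1% | 8.3% | 8.3% | about 0.2 |
| 10% | 12.3% | 12.8% | 12.8% | about 0.5 |
| 30% | 30.5% | 32.2% | 32.5% | about 2 |

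**Effect of fewer than six.** Let k phase I patients qualify, and keep the stated 3 and 19 new patients. The chance of at least one response at a true 30% is 1 - 0.7^(k+3); the maximum standard error is sqrt(0.25/(19+k)).

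| k | Stage-1 n | Chance at 30% | Total n | Maximum SE |
|---|---|---|---|---|
| 6 | 9 | 96.0% | 25 | 10.0% |
| 5 | 8 | 94.2% | 24 | 10.2% |
| 4 | 7 | 91.8% | 23 | 10.4% |
| 3 | 6 | 88.2% | 22 | 10.7% |

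As an illustration of the two-cycle condition, assume each of six patients independently has a 70-90% chance of reaching cycle 2. All six then qualify with probability 0.7^6 = 12% to 0.9^6 = 53%.

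**The case against.** The best defence has four parts.

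- **The default is the MTD.** Activity is one consideration among several, and no rule picks the dose with more responders. This stands: the selection figures are upper-end illustrations.
- **The discrepancy may be only wording.** Section 13.4 refers to available data, which could include response, and section 2.3 already says PK/PD may help determine the RP2D. This also stands in part. The passages are ambiguous rather than flatly opposed, but a reader cannot tell whether response may enter the choice.
- **Stage 1 still works.** A reader might infer that it loses its protection against an inactive drug. The documents do not support that: a trial with no responders still stops, and even under full selection 46-54% of trials stop at a true 5%. Passing stage 1 supports no efficacy claim, and the stated aim of not missing a 30% rate is not harmed by selection.
- **Nine is the governing number.** A reader might infer that stage 1 will be run with six patients. The text sets stage 1 at nine, and the three additional patients follow from assuming six. Stopping at six would breach the stated rule. What remains is that the plan does not say how to proceed when fewer than six qualify.

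**Conclusion.** The point holds in two limited parts. If response influences the choice of RP2D, the nine-patient binomial no longer describes stage 1, and the rule is weakened mainly at low true rates. The size rests on equal true rates, two candidate levels and a pick-the-higher rule, none of which the documents state. The inflation from this source is zero if the RP2D is the MTD or is lowered on toxicity alone. A reader might also infer that the primary rate is materially inflated. The added bias among passing trials does not support that: at most about 2 points at a true 30%, against a standard error of 9.2 points with 25 patients.

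Independently of selection, the counts of six, three and 19 are planning assumptions written as fixed numbers. If they were followed with three to five qualifying patients, the stated 96% and 10% standard error would not be met. This part rests on the documents' own cohort sizes and on their differing statements of which phase I patients count.

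**What to change.** 1. Reconcile the Study Design part of the synopsis with its Statistical Considerations and sections 13.1 and 13.4 on whether response data may enter the choice of RP2D.
2. Reconcile the Study Design part of the synopsis with its Statistical Considerations and sections 13.1 and 13.5 on which phase I patients count, and define k as the number at the RP2D who qualify. The definition should also agree with the response-evaluability rule in section 13.1, which accepts a CR/CRi after one cycle.
3. Replace the fixed numbers, including the schema footnote: stage 1 is filled to nine with 9 - k new patients, and the total to 25 with 25 - k. With k = 3 that means 6 new patients at stage 1 and 22 in all.
4. If response may inform the choice, report the CR/CRi rate and exact interval in the 25 - k patients enrolled after the RP2D was fixed, beside the pooled rate. Label the pooled rate as subject to selection, and state that the stage-1 pass probabilities no longer follow the nine-patient binomial.

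The cost is wording changes and one added analysis. Each phase I patient short of six adds one new patient beyond the 19. The separate estimate is less precise: at a 30% rate its standard error is sqrt(0.21/19) = 10.5% with 19 patients or sqrt(0.21/22) = 9.8% with 22, against sqrt(0.21/25) = 9.2% with 25.
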